#### **8.3 Determination of hematologic toxicity and CMV disease**

The most common grade  $\geq 3$  side effects on brentuximab after allogeneic transplant(7) are neutropenia (24%), and thrombocytopenia (20%) which were reversible. CMV was detected in 5 patients and was clinically significant in 1 patient.

Brentuximab will be discontinued if patient develops dual foscarnet and ganciclovir-resistant CMV viremia or histologic CMV end-organ disease. In addition, the study drug will be reduced in all future patients if at any time there is >25% grade IV neutropenia rate or >10% CMV disease rate attributable to treatment observed within Day 45- Day 180.

These rates will be monitored in a continuous fashion.

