## 4.0 Treatment Plan

### 4.1 Treatment Initiation:

Brentuximab will be given as an IV infusion over 30 minutes every 3 weeks for a total of 6 cycles. starting between days 35 and 60 post allogeneic SCT.

Brentuximab dose will be based on actual body weight starting with an initial dose of 1.2 mg/kg for the first 2 cycles and then the dose will be increased to 1.8 mg/kg after the second cycle for all subsequent cycles. Brentuximab dose will be based on actual body weight except for patients weighing more than 100 kg, then dose will be calculated based on 100 kg.

Patients must meet the following criteria to start any cycle of brentuximab:

1. Absolute neutrophil count > 1,000/mm^3 not requiring daily growth factor support on the day of the brentuximab infusion.
2. Platelet count greater than 50,000/mm^3 independent of platelet transfusions or thrombopoietin factor for at least 5 days.
3. No clinical evidence of life-threatening infection.

4. No active bleeding.
5. No uncontrolled acute GVHD (steroid refractory).
6. No CMV re-activation that is dual-refractory to foscarnet and ganciclovir/ No active CMV disease.
7. Creatinine < 1.5 mg/dL or creatinine clearance greater than or equal to 40 cc/min as defined by MDRD method from National Kidney Disease Education Program (NKDEP)
8. Serum bilirubin < 1.5 mg/dL
9. SGPT < 200 IU/L unless related to patient's malignancy

Vital sign monitoring, observation, and treatment of hypersensitivity reactions during and after infusion will be performed per standard of care.

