#### **4.2 Dose Modification:**

Dose will be reduced from 1.8 mg/kg to 1.2 mg/kg or from 1.2 mg/kg to 1 mg/kg or from 1 mg/kg to stop treatment if:

1. Neutropenia grade 3-4 unresponsive to G-CSF or grade 4 thrombocytopenia are observed.
2. Peripheral neuropathy, new or worsening grade 2 or 3. Withhold treatment until improvement or return to grade 1 or baseline; then resume with a dose reduction.

Dose will be reduced to 1 mg/kg if:

1. Creatinine clearance < 30 cc/min as defined by MDRD method from NKDEP.  
<http://nkdep.nih.gov/lab-evaluation/qfr/estimating.shtml>
2. Hepatic impairment defined as bilirubin > 2 mg/dL.

If the patient develops grade 3-4 neutropenia unresponsive to G-CSF: Hold until resolution to grade </= 1 and restart at lower dose.

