## 8.0 Statistical Considerations

Study Design

- 8.1 This is a phase II study in which brentuximab will be initiated after transplant (approximately day 35-60) post engraftment and restaging at day 30 (+10 days) and continued every 21 days for 6 cycles. Dose initiation will be at 1.2 mg/kg for 2 cycles and escalated to 1.8 mg/kg on subsequent 4 cycles. If greater than grade 3 toxicity seen at 1.2 mg/kg dose level then dose will be decreased to 1 mg/kg for all patients at initiation with subsequent cycles at 1.2 mg/kg dose. We will allow intrapatient dose modification based on toxicity.

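### The cohort dose-reduction rule in 8.3 counts CMV disease only from Day 45 to Day 180, although dosing may begin on Day 35 and a delayed sixth dose can fall after Day 180

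*Combined protocol and SAP*

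**What the plan says.** **The cohort trigger.** Section 8.3 reduces the drug in all future patients at a grade IV neutropenia rate above 25%, or at a more than 10% "CMV disease rate attributable to treatment observed within Day 45- Day 180". Both rates are monitored continuously. Section 8.2 labels transplant as Day 0, the only origin given for a day count. The day limit directly follows the CMV term. Whether it also governs the neutropenia rate is grammatically open.

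**Dosing.** Section 4.1 gives six cycles at three-week intervals, "starting between days 35 and 60 post allogeneic SCT"; 8.1 gives approximately the same start days. The first two cycles are at 1.2 mg/kg, then the dose is "escalated to 1.8 mg/kg on subsequent 4 cycles".

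**Delays.** Section 4.1 states: "Patients must meet the following criteria to start any cycle of brentuximab". One criterion is a platelet count above 50,000/mm³ "independent of platelet transfusions or thrombopoietin factor for at least 5 days". Section 4.2 reduces the dose if "Neutropenia grade 3-4 unresponsive to G-CSF or grade 4 thrombocytopenia are observed", and for unresponsive grade 3-4 neutropenia instructs: "Hold until resolution to grade </= 1 and restart at lower dose". Neither section caps the length of a delay.

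**Other protections.** Section 8.1 has a separate cohort rule with no day limit: "If greater than grade 3 toxicity seen at 1.2 mg/kg dose level then dose will be decreased to 1 mg/kg" for all patients at initiation. Evidence of CMV disease excludes a patient (3.2.4), and active CMV disease blocks any cycle (4.1, item 6). Sections 4.3 and 6.5 stop drug or end participation for dual-refractory CMV or CMV end-organ disease, on any day.

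**The concern.** A safety trigger should count events over the time patients are exposed. Here the counting period is fixed from transplant, while exposure starts anywhere in a 26-day range and has no fixed end. CMV disease that has been judged attributable to the drug is therefore left out of the rate if it falls before Day 45 or after Day 180.

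An uncounted attributable event can only lower the observed rate. With few patients, one case can decide whether the threshold is crossed, so the dose reduction for later patients could be missed or come late.

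**Working it through.** The plan gives no figure for this point (the confidence interval in 8.2 concerns graft failure), so the check is calendar arithmetic.

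**Inputs.** Start day s = 35 to 60 (4.1); six doses 21 days apart (4.1, 8.1); window Day 45 to Day 180 (8.3); Day 0 = transplant (8.2). Total delay d after the first dose is not given. Days are counted inclusively.

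**Formulas.**
- Dose 6 falls on Day s + 105 + d.
- Cycle 6 ends on Day s + 125 + d.
- Early uncounted days = max(0, 45 − s).
- Late uncounted days = max(0, s + 125 + d − 180).

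**On schedule (d = 0; 126 treatment days).**

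| Start day | Dose 6 | Cycle 6 ends | Early days lost | Late days lost | Days counted |
|---|---|---|---|---|---|
| 35 | 140 | 160 | 10 | 0 | 116/126 (92.1%) |
| 44 | 149 | 169 | 1 | 0 | 125/126 (99.2%) |
| 45 | 150 | 170 | 0 | 0 | 126/126 |
| 55 | 160 | 180 | 0 | 0 | 126/126 |
| 56 | 161 | 181 | 0 | 1 | 125/126 (99.2%) |
| 60 | 165 | 185 | 0 | 5 | 121/126 (96.0%) |

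The early loss lies wholly within cycle 1, at 1.2 mg/kg, where 8.1 already acts on toxicity above grade 3. What remains is mainly attributable CMV disease of grade 3 or lower.

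**With delay.** Dose 6 falls after Day 180 when s + 105 + d > 180, that is d > 75 − s:
- Day 60 start: d > 15 days.
- Day 35 start: d > 40 days.

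To show the range only, assume one delay of 21 days. Late uncounted days become s + 146 − 180 = s − 34, from 1 (Day 35 start) to 26 (Day 60 start), and dose 6 (Day s + 126) passes Day 180 for starts on Days 55 to 60. With 42 days, dose 6 falls on Day s + 147, which is Day 182 at the earliest, so it is outside the window for every start.

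**Dose in a delayed cycle.** Under 4.1 a platelet count at or below 50,000 delays a cycle, but 4.2 lowers the dose only for grade 4 thrombocytopenia. A delayed cycle can therefore still be given at 1.8 mg/kg, a level the 8.1 rule does not name. After a 4.2 hold for neutropenia the dose is lower and 8.1 may apply.

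**What one case can change.** Taking patients treated so far as the denominator (an assumption; 8.3 does not define it), the smallest count exceeding 10% is:
- 1 case in up to 9 patients (1/9 = 11.1%; 1/10 = 10.0% does not cross).
- 2 cases in 10 to 19 patients (2/19 = 10.5%; 2/20 = 10.0% does not cross).
- 3 cases in 20 patients (15.0%).

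This shows the consequence of a missed case, not how often one would occur.

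**The case against.** The strongest reply is that the gap is nearly empty. To be missed early, CMV disease must arise and be attributed to the drug within 1 to 10 days of a first dose at 1.2 mg/kg, in a patient with no active CMV disease when dosed. A short lag before counting could be deliberate. On schedule, the late days lost for a Day 60 start (Days 181 to 185) are 16 to 20 days after dose 6, against a conjugate half-life of about 4 to 6 days (9.2). A Day 35 start gains 20 counted days after cycle 6 ends. Day 180 also matches the six-month limit in 8.2 and the six-month visit in 5.4. The larger late losses depend on delays that no document quantifies.

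Most of this stands, and it is why the point is minor. It does not remove the point. The plan gives no reason for Day 45, and 8.3 already requires CMV disease to be attributable to treatment, so the cutoff removes only events already judged drug-related. A fixed Day 180 limit does not follow exposure when delay is uncapped.

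A reader might infer that early or late grade IV neutropenia is also ignored. That holds on one reading only; if the day limit applies to CMV disease alone, neutropenia has no gap. A reader might also infer that patients are left unprotected. They are not: 4.2, 4.3 and 6.5 have no day limit.

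**Conclusion.** A minor misalignment that is plain in the text. Starts on Days 35 to 44 lose 10 to 1 on-drug days from the CMV count. The on-schedule late loss is negligible (1 to 5 days, starts on Days 56 to 60). Dose 6 can fall outside the window only with total delay above 15 to 40 days, depending on start day. What is at risk is the timing or occurrence of the cohort dose reduction, and no other rule fully replaces it: 8.1 covers only toxicity above grade 3 at 1.2 mg/kg.

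This rests on counting days from transplant and on six cycles being given. The documents give no distribution of start days or delays, so the frequency is unknown and probably low. In particular, 15 of the 26 permitted start days have some uncounted time on schedule (10 early, 5 late), but this cannot be read as a proportion of patients.

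**What to change.** In 8.3, replace the Day 45 to Day 180 limit on CMV disease with: *observed from the first brentuximab dose to the later of Day 180 after transplant or the end of the last cycle given (21 days after the last dose)*.

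Add that grade IV neutropenia is counted over at least the same period. If no end date was intended for neutropenia, the new text should not create one.

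If a 30-day tail is preferred, word it as the later of Day 180 or 30 days after the last dose. A 30-day tail alone would shorten coverage: for a Day 35 start on schedule it would end on Day 140 + 30 = Day 170. Leave 8.2 unchanged.

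The cost is small. Slightly more events may count toward the trigger. The last blood count that section 5 schedules precedes dose 6 (5.2), so patients with a late or delayed dose 6 may need one extra. Follow-up to one year after treatment (6.7) already covers the longer window, but only for patients not taken off study earlier under 6.1 to 6.6.

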#### **8.4 Determination of incidence of GVHD and assessment of the effects of brentuximab on T cell populations (central and effector memory and naïve CD4 and CD8 cells) and serum CD30 levels both in subsets with and without GVHD**

Based on data published by Chen et al., (reviewed above) we hypothesize that down-regulation of CD30 may decrease the incidence of GVHD. We will perform immunological correlative studies on peripheral blood mononuclear cells (PBMC) and serum collected from patients at baseline (prior to initiation of brentuximab therapy) and on days 1, 3, and 5 after initiation of brentuximab and every 21 days thereafter to assess the effect on T cell subsets and their effector function as well as other immune subsets. We will also test both tissue and serum in patients who develop clinically significant GVHD.

#### **8.5 Determination of the response and complete response rates in patients with measurable disease after day +30 restaging and progression free and overall survival of this regimen**

Kaplan-Meier (1958) survival curves will be used to estimate overall survival and progression-free survival. Cox proportional hazards regression analysis may be used to model the association between overall survival and progression-free survival and disease and demographic covariates of interest.

## **9.0 Background Drug Information**

### **9.1 Mechanism of Action**

Brentuximab vedotin is an antibody drug conjugate (ADC) directed at CD30 consisting of 3 components: 1) a CD30-specific chimeric IgG1 antibody cAC10; 2) a microtubule-disrupting agent, monomethylauristatin E (MMAE); and 3) a protease cleavable dipeptide linker (which covalently conjugates

MMAE to cAC10). The conjugate binds to cells which express CD30, and forms a complex which is internalized within the cell and releases MMAE. MMAE binds to the tubules and disrupts the cellular microtubule network, inducing cell cycle arrest (G2/M phase) and apoptosis.

### **9.2 Pharmacodynamics/Kinetics**

Distribution: Mean steady state volume of distribution of approximately 6-10 L for ADC.

Metabolism: MMAE: Minimal, primarily via oxidation by CYP3A4/5

Half-life elimination: Terminal: ADC: ~4-6 days

Time to peak: ADC: At end of infusion; MMAE: ~1-3 days

Excretion: MMAE: Feces (~72%, primarily unchanged); urine

### 9.3 Current Indications:

#### 9.3.1 Hodgkin Lymphoma

Brentuximab vedotin is indicated for treatment of patients with Hodgkin lymphoma after failure of autologous stem cell transplant (ASCT) or after failure of at least two prior multi-agent chemotherapy regimens in patients who are not ASCT candidates.

#### 9.3.2 Systemic Anaplastic Large Cell Lymphoma

Brentuximab is indicated for treatment of patients with systemic anaplastic large cell lymphoma after failure of at least one prior multi-agent chemotherapy regimen.

### 9.4 Preparation and Storage:

9.4.1 Reconstitution: Reconstitute each 50mg vial of brentuximab with 10.5ml Sterile Water for Injection, USP, to yield a single-use solution containing 5mg/ml brentuximab vedotin. Direct the stream toward the wall of the vial and not directly at the cake or powder. Gently swirl the vial to aid dissolution. **DO NOT SHAKE.** The reconstituted solution should be clear to slightly opalescent, colorless, and free of visible particulates. Following reconstitution, dilute immediately into an infusion bag, or store the solution at 2-8°C (36-46°F) and use within 24 hours of reconstitution. **DO NOT FREEZE.** Discard any unused portion left in the vial.

9.4.2 Dilution: Calculate the required volume of 5mg/ml reconstituted brentuximab solution needed and withdraw this amount from the vials. Immediately add the reconstituted solution to an infusion bag containing a minimum volume of 100ml to achieve a final concentration of 0.4mg/ml to 1.8mg/ml brentuximab vedotin. The drug can be diluted into 0.9% Sodium Chloride Injection, 5% Dextrose Injection or Lactated Ringer's Injection. Following dilution, infuse the solution immediately.

9.4.3 Storage: The brentuximab vedotin solution may be stored at 2-8°C (36-46°F). **DO NOT FREEZE.** The solution must be used within 24 hours of reconstitution. The single-use vials should be stored in the original carton to protect from light at 2-8°C (36-46°F)

### 9.5 Administration

9.5.1 Administer only as an intravenous infusion over 30 minutes every 3 weeks

9.5.2 Do not mix brentuximab with, or administer as an infusion with, other medicinal products

### 9.6 Dosage form and strength

9.6.1 Brentuximab vedotin is available as single-use vials containing 50mg of brentuximab vedotin as a sterile, white to off-white lyophilized, preservative-free cake or powder.

### 9.7 Adverse Events

9.7.1 The most common adverse reactions (seen in  $\geq 20\%$  of patients) include neutropenia, anemia, thrombocytopenia, peripheral sensory neuropathy, fatigue, nausea, vomiting, diarrhea, pyrexia, rash, cough and upper respiratory tract infection

9.7.2 Serious but less common adverse reactions include serious infections and opportunistic infections, tumor lysis syndrome, progressive multifocal leukoencephalopathy (PML), Stevens-Johnson syndrome, and embryo-fetal toxicity.

